Specific Aim 2: Collect preliminary data comparing the usefulness of existing depression rating scales in characterizing participants and assessing depression treatment effects.

A variety of outcome measures of depression will be used to better assess their applicability and feasibility in the DS population. The relative performance of the scales will be evaluated based on their sensitivity to change and their association with clinical improvement ratings. Percent of item-level missing data, and any feedback on the appropriateness or ease of use of the scales from participants, including their legal guardians, or study personnel, will also be taken into account.

Specific Aim 3: Estimate the mean therapeutic dose of fluoxetine for adults with DS for treating major depressive disorder (MDD).

We will report the average dose of fluoxetine at the end of 16 weeks of treatment.

We expect our results to: 1) provide preliminary evidence on the safety, effectiveness, and tolerability of fluoxetine for the treatment of MDD in DS; 2) assess the relative performance of existing depression rating scales in DS; and 3) provide information on fluoxetine dosing. Currently there is no prospective evidence on the safety, efficacy, and tolerability of any medication for the treatment of depression in DS. The lack of evidence-based guidelines for the treatment of depression in DS likely contributes to the decreased awareness of and under/misdiagnosis of this largely treatable condition. Adults with DS and comorbid depression may be mistakenly diagnosed with dementia, another neuropsychiatric condition for which there is much greater awareness in DS, but few effective treatments.

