All subjects will have a baseline psychiatric diagnostic evaluation done to gather a thorough developmental, medical, and psychiatric history, as well as a mental status examination, and vital signs will be obtained for subjects evaluated in the clinic if subject cooperation allows. This will be determined by a board-certified psychiatrist experienced in the care of adults with developmental disabilities. Examples of lack of cooperation due to emotional dysregulation include refusal to participate, repeated requests for a break, and verbalizations of distress. Lack of cooperation may occur and is expected occasionally in this population. In visits where subject measures cannot be completed, measures from the caregiver will be collected only. In clinical care it is standard for caregivers to be the primary reporters of response to medication, therefore it is still valuable to collect non-primary outcome measures from the caregiver. Lack of cooperation would only become withdrawal of assent if behaviors stated in the assent section occur, for example regularly refusing to take the medication. If the visits are conducted remotely, not all vital signs will be obtained. The medical history will be aimed at ruling out other medical conditions that could exacerbate depression or behavioral symptoms (e.g., chronic gastrointestinal disease, obstructive sleep apnea, thyroid disease). The following standardized scales and testing may also be conducted. If cognitive testing has been completed within the past five years, these medical records may be requested and reviewed to inform study eligibility criteria.

- 1. Stanford-Binet Intelligence Scales, Fifth Edition (SB-5)** [33]. The SB-5 may be used to calculate an abbreviated battery IQ. The abbreviated IQ was chosen to limit subject burden given that a number of other measures will be conducted at screening.
- 2. The Wechsler Abbreviated Scale of Intelligence, Second Edition (WASI-II)** [34]. The WASI-II can also be administered remotely and will be used for subjects depending on age and ability.
- 3. Developmental Profile, Fourth Edition (DP-4)** [35]. If patients are unable to obtain a valid score on the SB-5 ABIQ or WASI-II due to constraints of a virtual visit or significantly delayed cognitive skills, the Cognitive and Adaptive Behavior subscales of the Developmental Profile (DP-4) Parent/Caregiver Interview Form may be administered. DP-4 scores will require a minimum age-equivalency cutoff of 24 months.

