Study medication will be prescribed to participants by the study's psychiatrist and the cost will be billed to their insurance following the same procedures as routine clinical care. The Lurie Center has clinical infrastructure including Medical Assistants and Nursing Staff to assist with Prior Authorizations as needed. We plan to prescribe a one-month supply of medication to mimic real-world clinical practice but can prescribe up to a three-month supply if required by insurance.

Outcome Measures:

1. **Montgomery-Asberg Depression Rating Scale (MADRS).** Change in MADRS total score between baseline and 16 weeks will be a secondary outcome measure. The MADRS is one of the most frequently used outcome measures in antidepressant efficacy trials and was developed to assess change in depressive symptoms after treatment with antidepressants [27]. The scale is clinician-rated and consists of 10 items, each rated on a 0-6 scale and summed to determine the total score. A total score of 7-19 is indicative of mild depression, 20-34 of moderate depression, 35-59 of severe depression, and 60 or greater of very severe depression. The MADRS will be conducted at screening, baseline, and each follow-up visit.
2. **Hamilton Depression Rating Scale (HAM-D).** Change in HAM-D total score between baseline and 16 weeks will be a secondary outcome measure. The 17-item HAM-D is one of the most frequently utilized outcomes measures in clinical trials for depression and is a clinician-rated scale with scores based on clinical interview and family report [28]. It addresses both somatic and psychological symptoms of depression. Items are rated on either a 5-point scale (0 to 4) or 3-point scale (0 to 2), where higher scores represent increasing severity of depression. The scores of the 17 items are summed to obtain a total score. The HAM-D will be optional and possibly conducted at baseline and each follow-up visit if time allows.

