3. **Glasgow Depression Scale for people with a Learning Disability (GDS-LD) and Carer Supplement (GDS-CS).** Change in GDS-LD total score and change in GDS-CS total score between baseline and 16 weeks will each be secondary outcome measures. The GDS-LD and GDS-CS were developed to describe and quantify depressive symptoms in adults with mild-to-moderate learning disabilities [29]. The GDS-LD consists of 20 items scored from 0 to 2. The GDS-CS consists of 16 items scored from 0 to 2. The 20 and 16 item scores are summed to obtain GDS-LD and GDS-CS total scores respectively. Higher scores are indicative of more severe depression. The GDS-LD and GDS-CS will be conducted at baseline and each follow-up visit. The GDS-LD and GDS-CS will be secondary outcome measures.
4. **Pittsburgh Sleep Quality Index (PSQI).** Change in PSQI total score between baseline and 16 weeks will be an exploratory outcome measure. The PSQI is a self-rated 19-item questionnaire which assesses sleep quality and disturbances over a one-month time interval [30]. It will be used to assess the sleep quality of study participants by parent/caregiver report.
5. **Clinical Global Impressions (CGI).** The percentage of subjects who respond to treatment, with response defined as a 16-week CGI-I rating of 1 or 2, will be the primary outcome measure. A trained clinician will perform the CGI. The CGI is designed to take into account all factors to arrive at an assessment of symptom severity and response to treatment, including parent report, parent-rated measures, and clinician-rated measures (as described below) [31]. The CGI Severity (CGI-S) item is rated on a scale from 1 to 7 (1 = normal, not at all ill; 2 = borderline ill; 3 = mildly ill; 4 = moderately ill; 5 = markedly ill; 6 = severely ill; 7 = among the most extremely ill patients). The CGI Global Improvement (CGI-I) item is also rated from 1 to 7 (1 = very much improved; 2 = much improved; 3 =

minimally improved; 4 = no change; 5 = minimally worse; 6 = much worse; 7 = very much worse). Clinically meaningful improvement will be defined as a CGI-I rating of 1 or 2. The CGI-S will be conducted at screen, baseline and the last follow-up visit. The CGI-I will be conducted at each follow-up visit.

Safety Monitoring:

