#Screen and Baseline Visits may be combined into a single visit if subject clearly meets eligibility criteria.
^Telephone Visit; ^^In clinic; ^^^In clinic, Zoom, or telephone; **Administered when emotional regulation, cognitive, and communicative abilities allow; [1] Parent or primary caretaker ratings; [2] SCID-5 = Structured Clinical Interview for DSM-5; [3] MADRS = Montgomery-Asberg Depression Rating Scale; [4] HAM-D = Hamilton Depression Rating Scale; [5] GDS-CS = Glasgow Depression Scale for people with a Learning Disability Carer Supplement; [6] PSQI = Pittsburgh Sleep Quality Index; [7] Females of child-bearing potential only; [8] genetic testing or clinical diagnosis; [9] CGI-S = Clinical Global Impression for Severity; [10] CGI-I = Clinical Global Impression for Improvement; [11] Suicide Assessment included in Adverse Effect Review; [12] Columbia-Suicide Severity Rating Scale (C-SSRS) will only be administered to participant and/or parent if any positive suicidal ideation is reported on Health/Behavior Review (screen) or Adverse Effects Review (baseline and all subsequent visits). Each visit following the first report of suicidal ideation will include the administration of the C-SSRS.

Drug Compliance

Families will be asked to return drug diaries within 5 business days of the scheduled Week 2, 4, 6, 8, 10, 12, and 16 visits. The study coordinator and/or PI will calculate drug compliance based on the number of missed doses between visits. Adequate compliance will be defined as $\geq 70\%$ of doses. If compliance falls

below this threshold and/or drug diaries are not returned, the subject may be discontinued from the study, per PI discretion.

7. Risks and Discomforts

Overall, the risk to the subjects in this research are essentially no different from those that would exist in standard clinical practice, but the research proposed offers considerable promise in improving our understanding of the treatment of depression in individuals with Down syndrome. Foreseeable risks and discomforts include:

Drug-free washout interval

Withdrawal of a medication prior to the study will only be pursued in cases for which the current medication is not effective or is causing intolerable side effects. In collaboration with the prescribing clinician, the medication will be gradually tapered according to best clinical practices with close monitoring for symptom worsening.

Fluoxetine Treatment

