We will estimate percentage response to fluoxetine treatment, and corresponding 95% confidence interval, for adults with DS using the proportion of participants with CGI-I scores ≤ 2 at 16 weeks. Participants with missing 16-week CGI-I scores will be treated as non-responders. Frequency of all side effects and adverse events and corresponding 95% confidence intervals will be tabulated. Percent tolerating treatment and corresponding 95% confidence intervals will be estimated using the proportion of participants who did not withdraw from the study before 16 weeks due to reasons other than side effects or an adverse event who discontinue treatment due to side effects or an adverse event. We will also use the 16-week study retention rate and corresponding 95% confidence interval, calculated as the proportion of the participants enrolling in the study who remain in the study for 16 weeks, as a measure of feasibility.

To estimate changes in depression scale scores, including the MADRS, HAM-D, GDS-LD, and GDS-CS, we will use repeated measures linear regression models, as implemented in PROC MIXED in SAS and fit using REML estimation, with repeated measurements of clinical scores as outcomes and time, in categories, as the predictor. We will allow unstructured covariance between repeated measurements from the same participant. Our primary interest will be only in the difference between baseline and week 16 scores, but all observed scores will be included as outcomes, given that partially observed scores may be informative for estimation. We will obtain an estimate of 16-week change and corresponding 95% confidence interval using a contrast of the week 16 and baseline model parameters. Sensitivity to change will be compared between scales using standardized effect sizes, calculated using the model-estimated 16-week change in each outcome divided by 1) the model-estimated standard deviation of the outcome at baseline and 2) the model-estimated standard deviation of the change score. Spearman correlations will quantify the strength of association between change in depression scale score and CGI-I ratings among those with observed 16-week data. We will also tabulate and compare the percent of item-level missing data for each scale.

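### Aim 2 compares four depression scales, each on its own observed data, although the GDS-LD and the optional HAM-D may be obtained in only some participants; add a same-participant comparison and scale-level completion.

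*Combined protocol and SAP*

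**What the plan says.** **The comparison.** Specific Aim 2 (section 2) is comparative: "The relative performance of the scales will be evaluated based on their sensitivity to change and their association with clinical improvement ratings". The statistical analysis plan in section 9 names the scales: "To estimate changes in depression scale scores, including the MADRS, HAM-D, GDS-LD, and GDS-CS". Each scale's scores go into a repeated-measures model using all observed values. The estimated 16-week change is divided by the baseline SD and, separately, by the SD of change. "Sensitivity to change will be compared between scales using standardized effect sizes". Spearman correlations between scale change and the CGI-I use participants with observed week-16 data.

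**Who gets each scale.**
- HAM-D (section 6, Outcome Measures): "The HAM-D will be optional and possibly conducted at baseline and each follow-up visit if time allows".
- GDS-LD: listed in Table 1 only under subject assessments, with the footnote "Administered when emotional regulation, cognitive, and communicative abilities allow". The Outcome Measures text carries no such condition: "The GDS-LD and GDS-CS will be conducted at baseline and each follow-up visit".
- MADRS and GDS-CS: both have a caregiver row in Table 1 without the ability condition. The HAM-D also has a caregiver row, marked optional.
- Fallback (section 6, Baseline Characterization): "In visits where subject measures cannot be completed, measures from the caregiver will be collected only".

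**Missing data on the scales.** Section 9 states: "We will also tabulate and compare the percent of item-level missing data for each scale". Aim 2 also takes account of feedback from participants, guardians and staff on how suitable and easy to use the scales are.

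The plan names no common participant set for the comparison, no paired analysis and no count of participants per scale.

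**The concern.** Two scales can be compared fairly on responsiveness only if they are measured in the same people, or if the people missing one scale resemble those who have it. The plan secures neither. Whether a GDS-LD is obtained depends on emotional regulation, cognition and communication, and any of these may be related to how much a participant improves or how much improvement can be recorded.

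The mixed model does not repair this. It uses a participant's other visits on the same scale, but someone never given the scale has no row in that scale's model. The CGI-I correlations have the same feature, since each would rest on whoever has that scale at week 16.

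The missing-data summary leaves a related gap. Section 9 gives no denominator for item-level missingness, so it is unclear whether a form never given counts as all items missing or drops out of the table. Section 10 has the clinician check that required items are complete before data entry, which would tend to keep item-level missingness low on forms that were given.

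Section 2 expects Aim 2 to show which existing scales can detect depression in Down syndrome and respond to treatment. A difference due to who was assessed could be read as a property of the instrument.

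**Working it through.** **1. The plan's own precision figure.** Section 9 (Sample Size Considerations) gives a 95% half width of 0.6 SD for mean change, with N = 20, 70% completion and a correlation of 0.5.
- SD of change = √(2(1 − 0.5)) = 1.0 baseline SD.
- Completers = 20 × 0.70 = 14.
- Half width = t(0.975, 13)/√14 = 2.160/3.742 = 0.577, which rounds to 0.6.

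The figure reproduces if all 14 completers have the scale. With 10, 8 or 7 of the 14 it becomes 0.72, 0.84 or 0.93 SD.

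**2. Effect of unequal availability on the comparison.** The documents give neither the share lacking each scale nor how their change differs, so both are assumptions. Let f be the share with the scale, and d the difference in mean change between those with it and those without. Take an overall mean change of 1 and an SD of change of 1. The standardized change among those with the scale is

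(1 + (1 − f)d) / √(1 − f(1 − f)d²).

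A scale obtained in everyone shows 1.00. For f = 0.6:

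| Size of d (SD) | Those assessed improve more | Those assessed improve less |
|---|---|---|
| 0.3 | 1.12/0.989 = 1.13 | 0.88/0.989 = 0.89 |
| 0.5 | 1.20/0.970 = 1.24 | 0.80/0.970 = 0.83 |
| 0.8 | 1.32/0.920 = 1.43 | 0.68/0.920 = 0.74 |

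For f = 0.5 with those assessed improving more, the values are 1.16, 1.29 and 1.53. With d = 0 there is no distortion at any f.

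These values are for the effect size based on the SD of change. For the baseline-SD version, if the baseline SD is the same in both groups and equal to the SD of change (as the plan's correlation of 0.5 implies), only the numerators matter: 1.12, 1.20, 1.32, or 0.88, 0.80, 0.68.

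**3. Does comparing in the same participants remove it?** Simulation: 14 completers, two equally responsive scales with true standardized change 0.8, scale changes correlated 0.6 to 0.8, and those with the second scale improving 0.5 SD more.

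| Have the second scale | Mean gap, all observed | Restricted scale looks better | Mean gap, same participants | Restricted scale looks better |
|---|---|---|---|---|
| 10 of 14 | 0.21 | 67–70% of trials | 0.00 | 50% |
| 7 of 14 | 0.38–0.39 | 74–75% of trials | 0.00 (within 0.01) | 50% |

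If availability is unrelated to change, the all-observed gap is only 0.02–0.03 (10 of 14) or 0.07 (7 of 14), a small-sample effect.

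**4. Precision of the matched comparison.** Simulation with no selection: 14 completers, 8 with the second scale, true standardized change 1.0. The SD of the between-scale difference, all-observed versus matched, is:
- about 0.44 to 0.45 versus 0.34 at correlation 0.9;
- 0.52 versus 0.53 at 0.7;
- 0.55 versus 0.59 at 0.6.

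Matching helps precision when the scales move closely together and costs a little when they do not.

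**The case against.** Much of the case on the other side stands, and it narrows the point.

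- **Direction.** A reader might infer that the plan favours the restricted scales. The documents do not support that. Nothing in them says whether those assessed improve more or less, and the reversed sign is equally compatible with the text.
- **HAM-D.** A reader might infer that the HAM-D, like the GDS-LD, goes only to the more able. It does not: it has a caregiver row in Table 1, and section 6 bases its scores on interview and family report. Its gate is time. Section 7 also lets families spread measures over several visits or complete them remotely. Selection on improvement is possible for the HAM-D, but no more than that.
- **Range of ability.** Severe and profound intellectual disability is excluded (section 4), and section 6 describes the GDS-LD as developed for mild-to-moderate learning disability. This narrows selection without removing it: section 5 still expects some participants to be unable to complete all assessments, and emotional regulation is a separate condition.
- **Feasibility.** It would be too strong to say that feasibility rests on item-level missingness alone, or that forms never given are certainly left out. Aim 2 also weighs user feedback. The fair criticism is that the denominator is undefined.
- **Weight.** The plan says the scales are compared. It sets no formal ranking, test or decision rule. Aim 2 is preliminary, and the primary outcome is untouched. With about 14 completers, the sampling SD of a between-scale difference (0.44 to 0.55 in step 4) exceeds the mid-case distortion of 0.24.

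The last point limits how much any comparison here can show. It does not justify leaving an avoidable source of difference in it.

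**Conclusion.** The concern holds in a limited form. The plan compares four scales, each on its own observed data, while its administration rules allow the GDS-LD and HAM-D to be missing for whole participants. No text puts the scales on the same people. Between-scale differences can therefore mix the instrument with the participants assessed.

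The size and direction are unknown. If 60% have the scale and their change differs by 0.3 to 0.8 SD, an equally responsive scale would show 1.13 to 1.43 or 0.89 to 0.74 against 1.00. The 60% and the 0.3 to 0.8 SD are assumptions with no source in the documents. If availability is unrelated to change, the loss is mainly precision.

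The point is strongest for the GDS-LD and weaker for the HAM-D. It bears on Aim 2 only.

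**What to change.** In section 9, Statistical Analysis Plan:

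1. Keep the all-observed model estimates as the description of each scale.
2. Add a between-scale comparison of effect sizes and CGI-I correlations in participants with baseline and week-16 scores on both scales. State that a difference will be attributed to the scales only if it holds in the same participants.
3. Report the number of participants with baseline and week-16 data on each scale.
4. Beside item-level missingness, report forms obtained out of forms scheduled, with the reason when not given (time, ability, cooperation). Say whether forms never given enter the item-level percentage.

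In section 6, reconcile the Outcome Measures text on the GDS-LD with the Table 1 footnote.

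**Cost.** SAP wording and one table; the scale scores are already planned, and the only new entry is the reason a form was not given. The pairwise sets are smaller and drop partially observed scores. Precision falls slightly when scale changes correlate at about 0.6. Conclusions apply only to participants who can complete both scales. Four scales give six pairs on possibly different sets, so the results need not form one consistent order. This is why the matched comparison belongs beside the all-observed estimates and does not replace them. The HAM-D can stay optional.

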APPENDIX A

Data Monitoring Committee / Data and Safety Monitoring Board Appendix

- *To be completed for studies monitored by Data Monitoring Committee (DMC) or Data and Safety Monitoring Board (DSMB) if a full DMC/DSMB charter is not available at the time of initial IRB review.*
- *DMC/DSMB Charter and/or Roster can be submitted to the IRB later via Amendment, though these are not required.*

A Data Monitoring Committee (DMC) or Data and Safety Monitoring Board (DSMB) will be convened for safety monitoring of this research study. The following characteristics describe the DMC/DSMB convened for this study (Check all that apply):

- The DMC/DSMB is independent from the study team and study sponsor.
- A process has been implemented to ensure absence of conflicts of interest by DMC/DSMB members.
- The DMC/DSMB has the authority to intervene on study progress in the event of safety concerns, e.g., to suspend or terminate a study if new safety concerns have been identified or need to be investigated.
- Describe number and types of (i.e., qualifications of) members:
Click or tap here to enter text.
- Describe planned frequency of meetings:
biannual
- DMC/DSMB reports with no findings (i.e., “continue without modifications”) will be submitted to the IRB at the time of Continuing Review.
- DMC/DSMB reports with findings/modifications required will be submitted promptly (within 5 business days/7 calendar days of becoming aware) to the IRB as an Other Event.
